### **7.7.2 Plasma Pharmacokinetic Parameters for ARRY-382 and its three metabolites (AR00469099, AR00469100 and AR00470870)**

PK parameters for patients in the PK set will be derived for ARRY-382 and its three metabolites (AR00469099, AR00469100 and AR00470870) on C1D1 and C2D1 when possible and appropriate. Parameters may include but not limited to  $AUC_{\tau}$ ,  $C_{max}$ ,  $T_{max}$ ,  $C_{trough}$ , accumulation ratio, and metabolite-to-parent ratio.

The individual plasma concentration-time data for each analyte will be evaluated with noncompartmental analysis (NCA) using Phoenix WinNonlin®, Version 8.0 or higher. Actual blood collection times and doses will be used for PK calculations. All BLQ values before the observed maximum plasma concentration ( $C_{max}$ ) will be set to 0; all BLQ values after  $C_{max}$  will be considered as missing. The AUC parameters will be calculated according to the linear-up log-down trapezoidal rule. Additional PK parameters may be calculated at the discretion of the pharmacokineticist.

All PK parameter values will be presented in data listings by phases, dose levels and cohorts for analyte, cycle and study day. Each parameter will be summarized in tables by phases, dose levels and cohorts for analyte, cycle and study day using the following descriptive statistics: n, arithmetic mean, standard deviation, CV, geometric mean, geometric CV, minimum, median and maximum. Summary descriptive statistics for in-text summary tables will include geometric mean with geometric CV for AUC,  $C_{max}$ , and  $R_{AUC}$ . For  $T_{max}$  and  $t_{1/2}$  values, median, minimum and maximum will be presented. Pharmacokinetic parameters will be excluded from the calculation of summary statistics if any of the above flags [a-c] apply.

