### **7.7.1 Plasma Concentrations of ARRY-382 and its three metabolites (AR00469099, AR00469100 and AR00470870)**

Plasma concentrations of ARRY-382 and its three metabolites (AR00469099, AR00469100 and AR00470870) will be collected and then determined using a validated bioanalytical method at the time points as specified in protocol. All plasma concentration values for each patient in the PK set will be included in the bioanalytical plasma concentration listings. Individual concentration records will be flagged for the affected visit if any of the following occur:

- a. Patient had vomiting within 4 hours following study drug administration on the day of series PK sampling.

- b. Plasma levels were not considered to be at steady-state (i.e. dosing was not performed for at least 4 consecutive days prior to C2D1).
- c. Subject received a higher or lower dose compared to planned treatment.
- d. PK sampling time was outside the allowed window or the elapsed time was not calculable.

The plasma concentrations of ARRY-382 and its three metabolites (AR00469099, AR00469100 and AR00470870) will be summarized by phases, dose levels and cohorts for all nominal time points, including predose (trough) concentrations for C1D15, C3D1, C4D1, C5D1 and C6D1, using the following descriptive statistics: n (number of patients with non-missing values), m (number of non-zero concentrations), arithmetic mean, standard deviation, coefficient of variation (CV), geometric mean, geometric standard deviation, geometric CV, minimum, median and maximum. An individual concentration-time data point be excluded from the calculation of summary statistics if any of the above flags [a-d] apply. For each time point, statistical values will only be calculated if at least two-thirds of the individual concentration data measured are above the limit of quantitation. BLQs will be set to zero for the calculation of arithmetic mean, SD, CV, minimum, median and maximum. For the calculation of geometric means and geometric CVs, BLQ concentrations will be replaced by  $\frac{1}{2}$  LLOQ. When greater than one-third of data points are BLQ, the means, standard deviations and CVs will be reported as not calculated (NC). When all data points are BLQ, the mean will be reported as BLQ and standard deviations and CVs will be reported as NC. If there are less than 3 values for calculation of standard deviation or CV, the value will be reported as NC.

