**Table 5: Definitions of Pharmacokinetic Parameters**

PK Parameter	Definition
C1D1	
AUC 0-8	Area under the plasma concentration-time curve from zero to 8 hours after drug administration
AUC last	Area under the plasma concentration-time curve from zero to the last measurable time point
C max	Maximum observed plasma concentration after drug administration
T max	Time to reach C max
T last	Time of last PK sample
MR Cmax	Ratio of C max values of the metabolite compared to parent, corrected for molecular weight.
MR AUClast	Ratio of AUC last values of the metabolite compared to parent, corrected for molecular weight.
C2D1	
AUC 0-8,ss	Area under the plasma concentration-time curve from zero to 8 hours after drug administration at steady-state
AUC last,ss	Area under the plasma concentration-time curve from zero to the last measurable time point at steady-state
AUC tau,ss	Area under the plasma concentration-time curve over a dosing interval at steady-state To estimate AUC tau,ss , the concentration measured at predose on steady state (C1D15 for Phase 1b/Part A and Phase 2) will be imputed as the concentration at the end of the dosing interval (i.e., 12 or 24 hours, as appropriate) assuming steady-state has been attained
C max,ss	Maximum observed plasma concentration after drug administration
C trough,ss	Measured concentration at the end of a dosing interval at steady-state
T max,ss	Time to reach C max
T last,ss	Time of last PK sample
MR Cmax,ss	Ratio of C max,ss values of the metabolite compared to parent, corrected for molecular weight.
MR AUCtau,ss	Ratio of AUC tau,ss values of the metabolite compared to parent, corrected for molecular weight.
R AUC	Accumulation ratio, calculated as: AUC 0-8,ss / AUC 0-8
R Cmax	Accumulation ratio, calculated as: C max,ss / C max

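### Trough-based PK parameters keep mistimed predose samples that the concentration summaries drop, and the SAP does not say whether a C1D1 flag carries over to the accumulation ratios

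*SAP*

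**What the plan says.** SAP 7.7.1 sets flags at the level of the sample: "Individual concentration records will be flagged for the affected visit if any of the following occur". The four flags are:

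- **a:** "Patient had vomiting within 4 hours following study drug administration on the day of series PK sampling"
- **b:** not at steady state, explained as "dosing was not performed for at least 4 consecutive days prior to C2D1"
- **c:** a dose above or below the planned one
- **d:** "PK sampling time was outside the allowed window or the elapsed time was not calculable"

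For concentration summaries, which include the C1D15 and C3D1–C6D1 troughs, the rule is "An individual concentration-time data point be excluded from the calculation of summary statistics if any of the above flags [a-d] apply". For parameters, SAP 7.7.2 narrows it: "Pharmacokinetic parameters will be excluded from the calculation of summary statistics if any of the above flags [a-c] apply". The same section bases the noncompartmental analysis on actual collection times.

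Table 5 of the SAP defines Ctrough,ss as "Measured concentration at the end of a dosing interval at steady-state". For AUCtau,ss, the C1D15 predose concentration "will be imputed as the concentration at the end of the dosing interval". R_AUC and R_Cmax are in the C2D1 block of that table but divide C2D1 values by C1D1 values.

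**The concern.** The actual-time analysis is a good reason to leave flag d out for most parameters: a sample drawn late is simply used at its true time. That reason fails where the method discards the true time. AUCtau,ss assigns a predose value to the end of the interval, and Ctrough,ss reports a predose value as the end-of-interval level with no time adjustment. MR_AUCtau,ss inherits whatever is in AUCtau,ss. So the plan can judge one C1D15 sample unfit for the trough table and still use it inside AUCtau,ss.

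The accumulation ratios raise a different question. Flags belong to a visit, while R_AUC and R_Cmax draw on two visits. Nothing states which visit's flags govern the ratio, so two programmers could handle the same patient differently.

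AUCtau, Ctrough and the accumulation ratio are named secondary endpoints in Part A and in all three Phase 2 cohorts (SAP 4.2). Part A dose groups had 6, 7 and 6 patients (Protocol 2.3.1), so one patient is visible in a summary.

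**Working it through.** The documents give no figure to reproduce. The first step is a reading of the rules; the arithmetic is an illustration of size.

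**1. Which parameters lose the true time**

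| Parameter | Does the actual draw time enter? | Is omitting flag d sound? |
|---|---|---|
| AUC0-8, AUClast, Cmax, Tmax | Yes (SAP 7.7.2) | Yes, when the time is known |
| Ctrough,ss | No, read as the end-of-interval level | No |
| AUCtau,ss | No, for the value placed at the end of the interval | No |
| MR_AUCtau,ss | No, inherited | No |

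Serial sampling stops at 8 h (Protocol 7.4), so any end-of-interval value must come from a predose sample.

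**2. Inputs for the illustration**

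- Half-life 18–19 h and Tmax about 2 h, from Study 101 (Protocol 2.2.2.2).
- Dosing interval 24 h; predose window 120 minutes before the dose (Protocol 7.4).
- Assumed: one-compartment oral model at steady state, with the absorption rate set so that single-dose Tmax is 2 h (ka = 2.018 /h at 18 h, 2.051 /h at 19 h); concentrations in units of absorbed dose over volume.
- AUC by linear-up log-down (SAP 7.7.2) on 0, 1, 2, 4, 8 and 24 h.

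**3. Predose sample drawn early**

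Absorption is complete by then, so the Ctrough,ss ratio is 2^(hours early / half-life):

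- 4 h early: 2^(4/19) = 1.157 to 2^(4/18) = 1.167
- 12 h early: 2^(12/19) = 1.549 to 2^(12/18) = 1.587

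For AUCtau,ss only the 8–24 h segment changes: 16 × (C8 − C24) / ln(C8/C24). At half-life 18 h, C8 = 1.2421, the true C24 = 0.6708 and the total AUC = 25.80.

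- True segment: 16 × 0.5713 / 0.6161 = 14.84
- With the 12-h-early value 1.0648 in place of C24: 16 × 0.1773 / 0.1540 = 18.42
- Ratio: (25.80 − 14.84 + 18.42) / 25.80 = 1.139

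| Sample drawn | Ctrough,ss ratio | AUCtau,ss ratio |
|---|---|---|
| 2 h early (permitted) | 1.08 | 1.02 |
| 4 h early | 1.16–1.17 | 1.04 |
| 6 h early | 1.25–1.26 | 1.06 |
| 12 h early | 1.55–1.59 | 1.13–1.14 |
| 1–6 h after the dose, if kept | 1.9–2.3 | 1.21–1.29 |

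In a cohort of six with one affected patient, the geometric mean Ctrough,ss is multiplied by 1.157^(1/6) = 1.025 to 1.587^(1/6) = 1.080 for 4–12 h early. For AUCtau,ss it is 1.040^(1/6) = 1.007 to 1.139^(1/6) = 1.022.

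No figure is given for MR_AUCtau,ss. The mistimed sample enters numerator and denominator, and the documents give no metabolite half-lives.

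**4. Accumulation ratios**

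If a fraction f of the first dose is lost to vomiting and the ratio is kept, R_AUC is multiplied by 1/(1 − f): 1.33 at f = 0.25, 2.0 at f = 0.50, 4.0 at f = 0.75. One such patient in six at f = 0.50 multiplies the geometric mean by 2^(1/6) = 1.12. These values of f are assumptions, and the result applies only under the reading that keeps the ratio.

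**The case against.** **The definitions already bar the worst case.** Table 5 asks for a predose or end-of-interval concentration, and a sample known to be post-dose is neither. Parameters are also derived only when possible and appropriate. This largely stands, so the post-dose row is an upper illustration and not the expected case. It does not cover a sample drawn too early, which is still predose, or one whose time is unknown.

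**Vomiting is already handled.** A reader might infer that the SAP retains an accumulation ratio built on a vomited first dose. The text does not support that. Vomiting is flag a, which lies inside the a-to-c exclusion, so C1D1 AUC0-8 and Cmax are themselves excluded, and the rule can be read to reach a ratio formed from them. What is left is silence on carry-over.

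**The errors are not all upward.** A reader might also infer a consistent overstatement of exposure. Early and post-dose draws do raise the value, but a time that cannot be calculated has no known direction. A trough collected while ARRY-382 is on hold, which Tables 10 and 11 of the Protocol provide for, would tend to be low.

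**Flag d can hit a good trough.** Doses are about 24 ± 2 h apart (Protocol 6.2.1). A sample at 23.5 h followed by a dose at 26 h is 26 − 23.5 = 2.5 h, or 150 minutes, predose: out of window, yet close to a true 24-h level. This is a real cost of the fix.

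**The consequence is small.** Trough concentrations by visit are already summarized with all four flags applied, individual values are listed, and Ctrough is not among the in-text parameters. All of this is correct, and it limits the point to descriptive secondary PK. AUC and R_AUC, however, are in-text parameters.

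**Conclusion.** The point holds for Ctrough,ss, AUCtau,ss and MR_AUCtau,ss. No stated rule removes a flag-d predose sample from them, although the same sample is removed from the concentration summary. Only general discretion could catch it, through the wording on when parameters are derived or the patient-level definition of the PK set (SAP 5.5), and neither is a prespecified sample rule.

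For an affected patient, a draw 4–12 h early gives Ctrough,ss 16–59% and AUCtau,ss 4–14% too high. A mislabelled post-dose draw, if kept, gives about 1.9–2.3 times and 21–29%. These sizes rest on the one-compartment model with Study 101 values. The documents give no basis for a frequency.

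For R_AUC and R_Cmax the supported statement is that the SAP does not specify whether a C1D1 flag carries over. The primary endpoints and the efficacy analyses are untouched.

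**What to change.** Amend SAP 7.7.2 so that exclusion follows the samples feeding each parameter:

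> Ctrough,ss, AUCtau,ss and MR_AUCtau,ss are also excluded if the predose sample used carries flag d. R_AUC and R_Cmax are excluded if flag a or c applies at C1D1 or C2D1, or flag b at C2D1. For all other parameters flags a–c apply.

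Simply widening the range to a–d would be worse. It would discard valid actual-time parameters and still leave open that AUCtau,ss uses a C1D15 sample and that the ratios use C1D1 denominators.

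The cost is a few lines of SAP text and its programming. A few patients lose a trough-based parameter or a ratio, including an occasional near-24-h sample flagged only because the next dose was late.

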**Table 5: Definitions of Pharmacokinetic Parameters**

PK Parameter	Definition
C1D1	
AUC 0-8	Area under the plasma concentration-time curve from zero to 8 hours after drug administration
AUC last	Area under the plasma concentration-time curve from zero to the last measurable time point
C max	Maximum observed plasma concentration after drug administration
T max	Time to reach C max
T last	Time of last PK sample
MR Cmax	Ratio of C max values of the metabolite compared to parent, corrected for molecular weight.
MR AUClast	Ratio of AUC last values of the metabolite compared to parent, corrected for molecular weight.
C2D1	
AUC 0-8,ss	Area under the plasma concentration-time curve from zero to 8 hours after drug administration at steady-state
AUC last,ss	Area under the plasma concentration-time curve from zero to the last measurable time point at steady-state
AUC tau,ss	Area under the plasma concentration-time curve over a dosing interval at steady-state To estimate AUC tau,ss , the concentration measured at predose on steady state (C1D15 for Phase 1b/Part A and Phase 2) will be imputed as the concentration at the end of the dosing interval (i.e., 12 or 24 hours, as appropriate) assuming steady-state has been attained
C max,ss	Maximum observed plasma concentration after drug administration
C trough,ss	Measured concentration at the end of a dosing interval at steady-state
T max,ss	Time to reach C max
T last,ss	Time of last PK sample
MR Cmax,ss	Ratio of C max,ss values of the metabolite compared to parent, corrected for molecular weight.
MR AUCtau,ss	Ratio of AUC tau,ss values of the metabolite compared to parent, corrected for molecular weight.
R AUC	Accumulation ratio, calculated as: AUC 0-8,ss / AUC 0-8
R Cmax	Accumulation ratio, calculated as: C max,ss / C max

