6.2 Study Drug Dispensing and Administration

6.2.1 ARRY-382

ARRY-382 oral capsules will be administered QD (approximately 24 ±2 hours) as a fixed dose either without food or after a light meal (e.g., breakfast) with approximately 240 mL of water. ARRY-382 should not be taken within 4 hours after a full meal because preliminary results

suggest a modest increase in exposure with larger meals ([Section 2.2.2.2](#)). Patients will be instructed not to crush study drug capsules.

The pharmacist or study nurse will ensure that the appropriate dosage is dispensed and will provide the patient with at least the appropriate number of capsules for the number of doses to be taken prior to the next scheduled visit.

Study site personnel will train the patient and/or the patient's caregiver on dosing procedures for the study drug. Patients will receive a diary to document self-administered dosing of study drug in each cycle to include the dose of study drug taken, the date and timing of dosing, if any doses were missed and the reason for the missed dose, and timing and type of meals eaten in relation to dosing. One diary will be provided per cycle. Patients will be instructed to return unused study drug and the patient diary to the site at each visit.

Complete dispensing instructions, dosing instructions (including the timing of study drug administration), dosing in relation to meals and instructions for missed doses will be provided in the Pharmacy Manual.

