7.4 Pharmacokinetic Assessments

Venous blood samples for measurement of plasma concentrations of ARRY-382 and its metabolites (AR00469099 [an N-oxide metabolite], AR00469100 [an N-desmethyl metabolite], and AR00470870 [a sulfate metabolite]) will be drawn at the time points specified in [Table 10](#) and [Table 11](#). Pembrolizumab concentrations are not planned to be measured because no drug-drug interaction is expected. However, remaining PK plasma samples may be used to assess pembrolizumab concentrations, CCI [REDACTED] or concomitant medications on an ad hoc basis. Complete instructions for sample collection, processing, handling and shipment will be provided in the Laboratory Manual.

Predose PK samples must be collected within 120 minutes prior to administration of ARRY-382. Postdose PK samples will be collected at 1 hr (± 5 min), 2 hr (± 10 min), 4 hr (± 20 min), and 8 hr (± 30 min) after administration of ARRY-382 on Cycle 1 Day 1 and Cycle 2 Day 1. Trough PK blood samples will be collected predose on Cycle 1 Day 15 and Day 1 of Cycles 3 through 6.

If a patient experiences an AE that results in an unscheduled visit or meets SAE criteria, a blood sample for measurement of plasma concentrations of ARRY-382 and its metabolites (AR00469099, AR00469100, and AR00470870) should be collected if less than 24 hours has elapsed since the last dose of study drug, if possible.

If vomiting occurs within 4 hours following study drug administration on the day of PK blood sampling, the time (using the 24-hour clock) of vomiting should be recorded on the transmittal forms that accompany the sample and that dose of study drug should not be re-administered.

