8.2.1.2 Subsequent Cycles

8.2.1.2.1 Subsequent Cycles Day 1 (± 2 days)

- ECOG PS
- Physical exam, including body weight
- Vital signs, including blood pressure, pulse, and temperature
- Serum or urine pregnancy test (females of childbearing potential only)
- Triplicate 12-lead ECG over a period of approximately 5 to 10 minutes (Cycle 2 only)
 - Predose and 4 hours postdose
- Single 12-lead ECG (all cycles subsequent to Cycle 2)
- Blood sample for the following tests:
 - Clinical chemistry, thyroid panel, hematology, and coagulation
 - 
 - Pharmacokinetics
 - Predose (i.e., within 120 minutes prior to administration of ARRY-382) and at 1, 2, 4, and 8 hours postdose (Cycle 2 only)
 - Predose (i.e., within 120 minutes prior to administration of ARRY-382) (Cycles 3, 4, 5, and 6)
- Urine samples for the following tests:
 - Urinalysis
 - 
- Tumor assessments, i.e., imaging (e.g., CT, MRI, x-ray, FDG-PET) and caliper measurements, as applicable (Cycle 3 Day 1 [± 7 days] and approximately every 6 weeks thereafter [e.g. Cycle 5 Day 1 [± 7 days], Cycle 7 Day 1 (± 7 days), etc.]
- Administration/dispensing of ARRY-382

- Administration of pembrolizumab
- Review of concomitant medications
- Review of AEs

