8.2.2.2 Subsequent Cycles

8.2.2.2.1 Subsequent Cycles Day 1 (\pm 2 days)

- ECOG PS
- Physical exam, including body weight
- Vital signs, including blood pressure, pulse, and temperature
- Serum or urine pregnancy test (females of childbearing potential only)
- Triplicate 12-lead ECG over a period of approximately 5 to 10 minutes (Cycle 2 only)
 - Predose and 4 hours postdose

- Single 12-lead ECG (all cycles subsequent to Cycle 2)
- Blood sample for the following tests:
 - Clinical chemistry, thyroid panel, hematology, and coagulation
 - 
 - Pharmacokinetics
 - Cycle 2 only: Predose (i.e., within 120 minutes prior to administration of ARRY-382) and at 1, 2, 4, and 8 hours postdose
 - Cycles 3, 4, 5 and 6: Predose (i.e., within 120 minutes prior to administration of ARRY-382)
- Urine samples for the following tests:
 - Urinalysis
 - 
- Tumor assessments, i.e., imaging (e.g., CT, MRI, x-ray, FDG-PET) and caliper measurements, as applicable (Cycle 3 Day 1 [± 7 days] and approximately every 6 weeks thereafter [e.g. Cycle 5 Day 1 [± 7 days], Cycle 7 Day 1 (± 7 days), etc.]
- Administration/dispensing of ARRY-382
- Administration of pembrolizumab
- Review of concomitant medications
- Review of AEs

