## **7.7 Pharmacokinetic Analysis**

The Pharmacokinetic Analysis Set will be used for all PK analysis, listings and figures. C1D1 is defined as single dose (i.e., first dose), and C2D1 is defined as steady state.

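### SAP Table 5 closes the Cycle 2 Day 1 AUCtau,ss with the Cycle 1 Day 15 trough, which understates AUCtau,ss for patients who missed doses just before Day 15

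*SAP*

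**What the plan says.** SAP Table 5 places AUCtau,ss under its C2D1 heading. To complete the interval, "the concentration measured at predose on steady state (C1D15 for Phase 1b/Part A and Phase 2) will be imputed" and is taken "as the concentration at the end of the dosing interval (i.e., 12 or 24 hours, as appropriate) assuming steady-state has been attained".

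Other passages bear on this rule:

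- **Steady-state day.** SAP 7.7 states that "C1D1 is defined as single dose (i.e., first dose), and C2D1 is defined as steady state".
- **C2D1 sampling.** Protocol 8.2.2.2.1 (Phase 2) schedules "Cycle 2 only: Predose (i.e., within 120 minutes prior to administration of ARRY-382) and at 1, 2, 4, and 8 hours postdose". Protocol 8.2.1.2.1 has the same scheme for Part A.
- **Trough-only sampling.** Protocol 7.4: "Trough PK blood samples will be collected predose on Cycle 1 Day 15 and Day 1 of Cycles 3 through 6". Footnote s of Protocol Tables 10 and 11 adds that these troughs are drawn even while ARRY-382 is on hold.
- **Flags.** SAP 7.7.1 flags concentration records for the visit concerned. Flag b, the steady-state flag, refers to the four days of dosing before C2D1. Flag c covers a dose above or below plan. SAP 7.7.2 drops parameters from summary statistics when flag a, b or c applies.
- **Dosing interval.** Protocol 6.2.1: "ARRY-382 oral capsules will be administered QD (approximately 24 ±2 hours) as a fixed dose".

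The documents give no reason for using the C1D15 trough rather than the C2D1 one.

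**The concern.** The C2D1 profile has samples at 0, 1, 2, 4 and 8 hours, so everything from 8 to 24 hours rests on the imputed end point. Using a predose value for that point is normal practice at steady state. The question is which predose value to use. The plan takes one from a different visit, while the sample belonging to the profile goes unused for this purpose.

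The checks do not clearly cover the borrowed sample. A patient whose drug was held around Day 15 still has a trough drawn, and Protocol Table 8 provides for resuming ARRY-382 after some holds at the same dose. If that patient is dosed normally over the four days before C2D1, flag b does not apply and the C2D1 profile looks sound. Its end point would nevertheless be a partly washed-out concentration.

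AUCtau and the metabolite-to-parent ratio are secondary PK endpoints in every cohort (SAP 4.2). Part A groups had 6 or 7 patients (Protocol 2.3.1), so one distorted value can move a group summary.

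**Working it through.** The documents give no AUCtau figure to reproduce. The mismatch is textual, and the calculation below only sizes it.

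**Inputs.** Median half-life 18 h (C1D1) and 19 h (C1D15) and Tmax about 2 h, from Study 101 (Protocol 2.2.2.2); midpoint 18.5 h used. QD dosing. C2D1 is Day 22. AUC by the linear-up log-down rule (SAP 7.7.2). **Assumption:** one-compartment oral model, concentrations in units of dose × F/V.

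**Model.**
- ke = ln 2 / 18.5 = 0.0375 per h.
- ka solves ln(ka/ke)/(ka − ke) = 2 h, giving ka ≈ 2.03 per h.
- Single dose: f(t) = ka/(ka − ke) × (e^(−ke·t) − e^(−ka·t)), summed over doses.
- 8–24 h segment = 16 × (C8 − C24) / ln(C8/C24).

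**Uninterrupted dosing.** By Day 15 the time elapsed is 14 × 24 = 336 h, or 336/18.5 ≈ 18 half-lives. Both predose values are 0.699. Concentrations at 0, 1, 2, 4 and 8 h are 0.699, 1.521, 1.576, 1.478 and 1.273, and AUC0–8 = 11.20. The 8–24 h segment is 16 × (1.273 − 0.699)/ln(1.273/0.699) = 15.32, so AUCtau = 26.52. That segment is 15.32/26.52 = 58% of the total. The two closures give a ratio of 1.000.

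**Doses missed just before C1D15, resumed on Day 15 after the predose draw.** By C2D1, C8 is back to 1.272, AUC0–8 to 11.20 and the predose value to 0.698. The C2D1 closure gives 26.50.

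| Days missed | C1D15 predose | 8–24 h segment | AUCtau, C1D15 closure | Ratio to C2D1 closure |
|---|---|---|---|---|
| 14 | 0.284 | 10.55 | 21.75 | 0.82 |
| 13–14 | 0.116 | 7.72 | 18.91 | 0.71 |
| 12–14 | 0.047 | 5.94 | 17.14 | 0.65 |
| 11–14 (extreme) | 0.019 | 4.78 | 15.97 | 0.60 |

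The errors are about −18%, −29%, −35% and −40%. For one to three missed doses, a half-life of 18 h gives ratios of 0.818, 0.711 and 0.645, and 19 h gives 0.823, 0.716 and 0.649. In these cases the modelled concentration 24 h after the C2D1 dose is 0.698 to 0.699, so the C2D1 predose closes the profile with essentially no error. All of these patients were dosed on Days 18–21, so flag b is not triggered.

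**Doses missed on Days 15–17, between the visits, and resumed on Day 18.** AUC0–8 = 11.08. The segment is 15.23 with C1D15, 15.05 with C2D1, and 15.16 with the modelled 24 h value. The totals are 26.31, 26.13 and 26.24, so the errors are +0.3% (C1D15) and −0.4% (C2D1). The choice makes almost no difference.

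**Effect on a group of six.** If all six contribute and one value is multiplied by 0.65, the geometric mean is multiplied by 0.65^(1/6) = 0.93, or about 7% low. With 0.82 it is 0.82^(1/6) = 0.97, or about 3% low.

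**The case against.** The strongest defence is that C1D15 is itself a steady-state trough under full dosing. It is about 18 half-lives in, Protocol 2.2.2.3.1 describes that time point in Study 101 as a steady-state trough, and Table 5 makes the rule conditional on steady state. That stands: for an adherent patient the rule does no harm.

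A reader might infer that any hold, reduction or interacting drug around the two visits spoils the parameter. The documents do not support that.

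- Holds between the visits that pass flag b make almost no difference, as shown above.
- Doses missed just before C2D1 favour the C1D15 trough (Day 21 missed: +8% against −14% with the C2D1 predose; Day 20: +3% against −4%), but flag b removes such profiles from the summaries.
- A reduced dose at C2D1 falls under flag c.
- Strong CYP3A inhibitors and inducers are prohibited (Protocol 6.5.3), and a stable interaction affects both troughs alike.

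A reader might also infer that a C1D15 trough drawn after missed doses would certainly be used. The text does not establish that. Flag c is not restricted to C2D1, parameters are derived only where appropriate, and the SAP does not say whether a C1D15 flag carries over to the C2D1 parameter. This is a gap in the specification, not proof of use.

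Finally, the SAP was written against protocol Version 5, and only Version 4 was available here. A change to the C2D1 schedule cannot be excluded, although the SAP still derives C2D1 parameters.

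**Conclusion.** The point holds in a narrow form and is minor. Table 5 uses a trough from another visit where the profile's own predose sample is scheduled, and the stated checks do not clearly protect against a bad one. The exposed case is doses missed or held just before C1D15 with normal dosing by C2D1. That patient's AUCtau,ss is then about 18%, 29% or 35% too low after one, two or three missed doses.

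The 40% figure for four missed doses is an illustrative extreme and should not be read as typical. These are per-patient errors under an assumed one-compartment model with half-life 18.5 h and Tmax 2 h. The documents give no frequency for the missed-dose pattern, so the effect on cohort summaries is unknown.

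MR_AUCtau,ss may also be affected, by an amount not quantified: parent and metabolite are closed with the same C1D15 sample, so the errors may partly cancel. R_AUC (from AUC0–8), R_Cmax and the primary endpoints are unaffected. Separately, the 12-hour alternative in Table 5 does not fit a study that doses only once daily.

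**What to change.** In SAP Table 5:

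1. Use the C2D1 predose concentration as the 24 h value for AUCtau,ss.
2. Allow the C1D15 predose value only when the C2D1 predose is missing and C1D15 passes a dosing check equivalent to flag b, applied to the days before C1D15.
3. Delete the 12-hour alternative for the end of the dosing interval.

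If C1D15 was chosen deliberately, give the reason, extend flag b to it, and state that a flag on the C1D15 record excludes the C2D1 AUCtau,ss and MR_AUCtau,ss. Before finalising, confirm that protocol Version 5 keeps the C2D1 predose sample.

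The cost is SAP wording and a small programming change. Under the Version 4 schedule no additional sample or visit is needed.
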